Confidentiality will be protected by having records identified by code number only with the master list including names kept in a sealed envelope in a locked file in the Principal Investigator's office and by the pharmacy. Subjects will be given telephone numbers to call in case of emergency, 24 hours a day.

12.1 Potential benefits of the proposed research to the subjects and others. There will be no direct benefit to subjects participating in this study. However, subjects will receive complete medical and psychological evaluation. Cigarette smokers will be given anti-smoking literature and treatment resources will be provided for smoking cessation.

12.2 Importance of the knowledge to be gained. This proposed study may help to develop new and more effective tobacco control policies. We believe that the risk/benefit ratio for this study is acceptable, and that the benefits of the proposed studies outweigh the potential risks to subjects.

12.3 Data safety and monitoring plan: The Principal Investigator will conduct a review of all adverse events and determine the attribution and grade of severity of the adverse event by using the following scales:

Attribution of Risk Categories:

Definite: Adverse event(s) will clearly be related to investigational agent(s) or other intervention

Probable: Adverse event(s) will likely be related to investigational agent(s)

Possible: Adverse event(s) may be related to investigational agent(s)

Unlikely: Adverse event(s) will doubtfully be related to investigational agent(s)

Unrelated: Adverse event(s) will clearly not be related to the investigational agents(s)

Grades of Risk:

0: No adverse event or within normal limits

1: Mild adverse event

2: Moderate adverse event

3: Severe adverse event resulting in hospitalization or prolongation of existing hospitalization, a persistent or significant disability/incapacity, or a congenital anomaly/birth defect

4: Life-threatening or disabling adverse event

5: Fatal adverse event

Serious adverse events (SAEs) include any untoward medical occurrence that at any dose results in death or the immediate risk of death, hospitalization or the prolonging of an existing hospitalization, persistent or significant disability/incapacity or a congenital anomaly/birth defect. Subjects will be terminated from participation if the investigator feels that subjects' health or well-being may be threatened by continuation in the study. Serious unanticipated and anticipated adverse events will be reported within 48 hours to the VA Hospital and Yale IRB, and NIDA. We will directly report to the FDA, whenever their magnitude or frequency exceeds expectations.

The risk associated with participating in this study is moderate, because nicotine administered may be associated with mild side effects. Serious side effects associated with this treatment are not expected. This project will be monitored by a Data and Safety Monitoring Board (DSMB) because the study involves double-blind treatment of smokers with nicotine. This board is composed of persons not otherwise affiliated with the clinical study who are experienced in various aspects of the conduct of clinical trials for the treatment of addictive disorders. We propose three investigators located here in Connecticut who are not directly involved in this study – [name]., [name]., and [name]. as the members of the DSMB. The members of the DSMB and all study Investigators will complete Conflict of Interest forms created by Yale's IRB in accordance with NIH guidelines.

In order for the DSMB to fulfill its mission of assuring the safety of human subjects and the scientific integrity of the studies conducted, the Board will have access to accumulating study outcome data in a manner that will protect its confidentiality and preserve its statistical integrity. The Board will examine accumulating data to assure that the risks and benefits of participation remain acceptable and that the results of the study will be considered scientifically reliable. The conditions under which the Board will examine this data are described below. This monitoring will be consistent with NIH policy regarding the protection of human subjects in research, and FDA guidance on statistical practices for clinical trials (ICH E9) and good clinical practices (ICH E6). In general, the data to be reviewed will include screening data, baseline data, efficacy data, and safety data.

The study will be monitored for safety in an ongoing way as well as three times each year formally by the DSMB. The P.I. will attend an initial part of this meeting to present the study's adverse events and ongoing subject accrual, as well as any potential study design changes under consideration. The remainder of the meeting will not include any direct study personnel until the end of the meeting, when the DSMB will convey directly to the P.I. any safety or study conduct concerns, as well as requests for potential interim analyses.

Following each DSMB meeting written minutes will be prepared and distributed summarizing any recommendations. These written reports will insure timely communication with the study P.I. with preparation of any protocol amendments necessary. After each DSMB meeting, this written report will describe all recommendations including additional safety steps. The FDA adverse drug experience reporting timelines will be utilized as timelines to disseminate feedback from the DSMB to the principal investigator and sub investigators. That is, three days for acute circumstances and ten days for non-acute circumstances.

13. Informed consent: Subjects will be recruited from the New Haven area by newspaper advertisements and fliers. Interested subjects will be informed about the study over the telephone and asked for current use of drugs and medical problems. If subjects are interested, they will then come into the clinic for a full screening evaluation. Upon arrival, a research assistant will review the detailed consent form and will ask questions to make sure that the subjects understand the procedure and their rights and informed consent will be obtained.

14. Information Security/Confidentiality: Confidentiality in this study is of the utmost importance to us. All information obtained will be stored in coded form.

Personally identifiable information (PII) and protected health information (PHI) that is obtained from subjects or about them will be protected by the research team who will follow all guidance provided in the following VHA HANDBOOKS and DIRECTIVE:

- VHA HANDBOOK 1605.1, PRIVACY AND RELEASE OF INFORMATION Dated May 17, 2006
- VHA HANDBOOK 1907.01, HEALTH INFORMATION MANAGEMENT AND HEALTH RECORDS Dated August 25, 2006
- VHA HANDBOOK 6500, INFORMATION SECURITY PROGRAM Dated September 18, 2007
- MEMORANDUM FOR UNDER SECRETARIES, ASSISTANT SECRETARIES AND OTHER KEY OFFICIALS, SUBJECT: Protecting Information Security and Privacy Dated February 27, 2009
- VHA HANDBOOK 1200.12, USE OF DATA AND DATA REPOSITORIES IN VHA RESEARCH Dated March 9, 2009

All data collected will be the property of the Department of Veterans Affairs whether in paper or electronic form and will be secured utilizing the following methods:

Paper:

- All paper documents will be stored on VA property unless authorized by the Director, Information Security Officer, and Privacy Officer in writing.
- All paper documents will be locked in an approved file cabinet with only members of the research team having access.

Electronic:

- All information in electronic form will be stored on VA servers behind the VA firewall.
- All portable media will meet or exceed FIPS 140-2 compliance and encryption. And will be approved in writing by the Information Security Officer.

The location(s) where information will be stored is (are) Building 35, rooms 19 and 39
The people or agencies that will have access to the information are the study investigators.

No information related to this research will be released to any third party or disclosed outside of the VHA – except as required or permitted by law.

Research records will have identifiers removed and will be stored with a code number linked to subjects. The code will not be derived from any personal identifiers. The key to the code will be kept in a locked file cabinet, located in Bldg 35, room 19. Subjects' identity will not be revealed in any reports or publications resulting from this study.

15. Location of Study: This study will be conducted in Ward G9W (the Biostudies Unit) located in Building 1 at the West Haven VA Medical Center.

16. Payment: Subjects will be paid cash; \$30 for participating in the screening and \$150 for each of the 5 lab sessions. In addition, to help offset transportation costs, subjects will be paid \$20 for each of the 5 lab sessions. If the subject is asked to return in addition to these 5 visits for any reason, they will be paid \$20 for travel. If the subjects choose to terminate a session prematurely, or a session is terminated early for medical reasons, they will receive full payment for that day. If they become ineligible to continue in the study due to non-compliance with study procedures, they will only be paid for the portions of the study in which they have participated. Subjects may be paid up to \$880.00 if all parts of the study are completed. Payment may exceed \$880.00 if the subject is asked to return in addition to the screening visit and the 5 lab sessions for any reason. The payment will increase by \$20 for each additional visit.

| Visits | Amount paid | Total |
|---|------------------------|----------------------------|
| Screening Visit | \$30.00 | 30.00 |
| Lab session | \$150 each lab session | Five lab sessions \$750 |
| Travel to each lab session | 20.00 each lab session | Travel for 5 session \$100 |
| | Max total | \$880.00 |
| If subject is asked to return for additional testing or visit | \$20 for travel | \$20.00 |

17. Funding Source: An R03 DA043004-01 grant from NIDA (pending).

18. Duration: The entire study will take approximately 2 years to complete.

19. References:

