Specific Aim: To determine the dose-effect curves for positive subjective effects (drug liking and good drug effects) and alleviation of smoking urges, as a function of nicotine delivery rate in menthol and non-menthol cigarette preferring smokers.

Hypothesis #1A: Positive subjective effects of nicotine will gradually decline with slower delivery rates, with minimal effects of nicotine delivery rate on urges to smoke.

Hypothesis #1B: Non-menthol smokers, compared to menthol smokers, will have greater responses to nicotine for these outcomes as reflected by a leftward shift in dose-effect curves.

Exploratory Aim #1: To explore the dose-effect curves of nicotine delivery rate for a) reinforcement (assessed with the monetary value of the dose from the Multiple-Choice Procedure (6), b) heart rate and blood pressure, and c) tobacco withdrawal severity (assessed with self-report symptoms and cognitive performance).

Exploratory Aim#2: To examine the impact of plasma nicotine levels and rate of nicotine metabolism (measured by plasma hydroxycotinine/cotinine ratio) on the dose-effect curves for the main study outcomes.

Exploratory Aim#3: To examine sex differences for the main study outcomes.

5. Background:

Nicotine control policies to reduce the addictive potential of tobacco products:

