Justification to include smokeless tobacco and e-cigarette users: We will include users of smokeless tobacco or e-cigarettes given the high prevalence of e-cigarette and smokeless tobacco products among young adults (26-28). As noted above, urine cotinine will be used to biochemically confirm the subjects' nicotine consumption and smoking status and used as a covariate in all analyses if required.

Subject sampling to account for sex, race, dependence symptoms, and smoking frequency: We are planning to enroll Caucasian and African-American smokers while maintaining an approximately equal male-to-female ratio.

We will create dichotomous variables to be used as a covariate to match groups on race (European American and African American) and sex because of the potential influence of race and sex on smoking behavior and nicotine pharmacokinetics (22, 29). We will also control for differences in the frequency of smoking because it may influence the behavioral effects nicotine (30-32); a continuous variable based on the reported smoking frequency (cigs per day) will be used as a covariate in the analyses if required.

8: Recruitment:

Hundred subjects will be recruited. The goal is to have 70 completers, 35 menthol and 35 non-menthol cigarette smokers.

9. Research Plan:

A. Overview

Experimental Summary: Subjects will complete five separate experimental sessions on five separate days with each session beginning around 8 AM (Fig 2). Each session (1 to 15 days apart) will include one infusion condition that will be either saline or nicotine at four different infusion rates. The five infusion conditions will be assigned randomly to one of the five experimental sessions. All infusions will last 10 minutes and be controlled by two infusion pumps, a saline infusion pump and a nicotine infusion pump. The 0.24 mcg/kg/s condition will include a 1 minute infusion of nicotine followed by a 9 min infusion of saline; the 0.096 mcg/kg/s condition will include a 2.5 minute infusion followed by a 7.5 min infusion of saline; the 0.048 mcg/kg/s condition will include a 5 min infusion of nicotine followed by a 5 min infusion of saline; the 0.024 mcg/kg/s condition will include a 10 min infusion of nicotine and no infusion of saline; and the placebo condition will include a 10 min infusion of saline and no

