infusion of nicotine. The most rapid nicotine infusion rate, 0.24 mcg/kg/s, has proven to be well tolerated in our prior studies (12, 18-20, 22). The total weight-adjusted nicotine dose will not exceed 1.2 mg. Subjects will complete baseline assessments after an indwelling catheter is inserted into an antecubital vein for safety and drug administration. Immediately prior to the start of the infusion (@ min 0) and at intervals following the start of the infusion, heart rate, blood pressure, DEQ and withdrawal assessments will be taken as shown in **Fig 2**. At the end of the session (min 120), subjects will complete the Drug versus Money Multiple-Choice Form (\$MCP) (23).

Session procedures: Before the experimental session, subjects will be required to abstain from smoking for 10h, which will be verified by expired air CO levels \leq 10 ppm (33, 34). Subjects will also be asked to refrain from consuming alcoholic beverages and drugs prior study participation, which will be verified by urine drug screening and breathalyzer before the sessions. Subjects that are non-compliant will be rescheduled or, if they are repeatedly non-compliant, discharged from the study. Subjects will be instructed to drink their typical amount of caffeinated beverages to minimize caffeine withdrawal, which could confound the study measures. Subjects will be instructed not to eat for 4 h before the sessions to minimize heartburn or nausea that can be associated with IV nicotine administration. A light meal will be provided at the end of each session.

Fig # 2 Schedule of Events: Experimental Session*

| Time point | Measures and Events |
|------------|--|
| Baseline | CO, urine and blood samples, HR/BP, M-NWSC, BQSU, SAFTEE, CPT |
| 0 min | IV Infusion starts |
| 1 min | HR/BP, DEQ, plasma nicotine |
| 3 min | HR/BP, DEQ, plasma nicotine |
| 5 min | HR/BP, DEQ, plasma nicotine |
| 8 min | HR/BP, DEQ, plasma nicotine |
| 10 min | IV Infusion ends, plasma nicotine |
| 11 min | HR/BP, DEQ, BQSU, plasma nicotine |
| 12 min | HR/BP, plasma nicotine |
| 13 min | HR/BP, DEQ, plasma nicotine |
| 15 | HR/BP, DEQ, plasma nicotine |
| 18 | HR/BP, DEQ, plasma nicotine |
| 20 | HR/BP, DEQ, plasma nicotine |
| 25 | HR/BP, DEQ, |
| 30 min | HR/BP, DEQ, BQSU, CPT, M-NWSC |
| 40 | HR/BP, DEQ, plasma nicotine |
| 50 | HR/BP, DEQ, plasma nicotine |
| 60 | HR/BP, DEQ, BQSU, M-NWSC CPT, plasma nicotine |
| 90 | HR/BP, DEQ, BQSU, M-NWSC CPT, plasma nicotine |

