Positive subjective effects of nicotine will be assessed with the “Like the Drug Effects” and “Good Drug Effects” items from the DEQ, consistent with the FDA Guidance on abuse potential assessment (10). These items have been shown to correlate with the abuse potential of drugs of abuse. Effects will be tested using linear mixed effects models with peak change on each DEQ item as a response variable, cigarette-preference (menthol vs. non-menthol) as a between-subject factor, nicotine delivery condition as a within-subject factor and their interaction. Period effects will be controlled for by including test day as an additional predictor in the models. Random effects for subject and condition within subject will be used to account for correlations between repeated measures. Because of the potential skewed distributions of the subjective effects data, transformations will be applied as necessary. We will evaluate the main and interactive effects of menthol cigarette preference and delivery rate. We anticipate statistically significant main effects of menthol-preference, nicotine delivery rate and a significant interaction between menthol-preference and nicotine delivery rate. To better understand the dose effects of nicotine delivery rate and whether they are moderated by menthol preference, we will construct specific contrasts among the four doses to test whether there is an indication of significant linear, quadratic, linear on log-scale or sigmoidal dose-response relationships across, or within menthol-preference groups. The possible dose-response curves identified by the specific mean contrasts will be compared by fitting linear and non-linear (as necessary) dose-response models with continuous dose and selecting the best-fitting model by the Akaike’s Information Criterion (AIC).

To test for an effect of delivery rate on smoking urges, assessed by the BQSU (Factor 1 and 2) scores, we will use similar modeling approach described for subjective effects but we will also include time as a within-subject factor with outcomes for minute 0, 10, 30, 60 and 120. We anticipate a significant main effect of menthol-preference, nicotine delivery rate and potentially a significant interaction between menthol-preference and nicotine delivery rate.

Rationale for sample size:

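### The planned BQSU test gives no decision rule for the urge half of Hypothesis #1A: minimal has no bound, and no contrast with saline is named

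*Combined protocol and SAP*

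**What the plan says.** Hypothesis #1A (section 4, Specific Aim) makes two predictions: "Positive subjective effects of nicotine will gradually decline with slower delivery rates, with minimal effects of nicotine delivery rate on urges to smoke". The second is a claim of near-absence.

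Section 10 analyses BQSU Factors 1 and 2 with an approach similar to that for the DEQ items. That approach has "nicotine delivery condition as a within-subject factor and their interaction" with cigarette preference. It adds contrasts: "we will construct specific contrasts among the four doses to test whether there is an indication of significant linear, quadratic" and other shapes. Linear and non-linear curves are then fitted and compared by AIC. For BQSU the plan adds time: "we will also include time as a within-subject factor with outcomes for minute 0, 10, 30, 60 and 120". The stated expectation is: "We anticipate a significant main effect of menthol-preference, nicotine delivery rate and potentially a significant interaction between menthol-preference and nicotine delivery rate".

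Saline is one of the conditions run. Section 9.A says: "The five infusion conditions will be assigned randomly to one of the five experimental sessions". The model text does not say whether saline is a level of the condition factor, though the two passages together make that the natural reading.

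The plan gives no margin, smallest effect of interest or interval rule for a minimal effect on urges. The sample-size text covers only detection of large effects (f=0.4 and f>0.5).

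The schedule in Fig 2 has BQSU at baseline, 11, 30, 60, 90 and 120 minutes, with rows such as "11 min | HR/BP, DEQ, BQSU, plasma nicotine" and "90 | HR/BP, DEQ, BQSU, M-NWSC CPT, plasma nicotine". The analysis uses 0, 10, 30, 60 and 120.

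**The concern.** A difference test is being asked to support a claim of little or no difference.

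- **A significant condition effect** may mean only that nicotine differs from saline, which says nothing about rate.
- **A non-significant effect** may mean only that the test missed a real difference.
- **Flat contrasts among the active rates** are what one would see if every rate relieved urges equally, and also if none did.

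Section 6 (Significance) argues that a slow-delivery product might carry low addiction liability and still relieve urges. Falling liking with flat urge curves supports that argument only if the rate effect is bounded and the slowest rate relieves urges more than saline. The design collects the data for both checks, but the plan specifies neither. Change from baseline cannot replace the saline comparison: the preliminary urge results in section 5 compare end of session with baseline, so they do not separate nicotine from the passage of time.

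**Working it through.** **Inputs.** N=56 is 2 × 35 × (1 − 0.20), from the sample-size rationale. N=70 is the completer goal in section 8. Alpha is 0.025 (section 10), taken as two-sided because the plan does not say. The BQSU SD and the correlation between sessions (ρ) are not given, so results are in SD units for assumed ρ of 0.3 to 0.7. Paired values are N=56 / N=70.

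**The plan's own figure.** The 31 per group for the menthol effect (d=0.8, alpha 0.025) reproduces by noncentral t, with power 0.800. There is no corresponding figure for a minimal rate effect on urges.

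**1. Significant condition effect when rate does nothing.** Put saline at 0 and all four rates at 0.5 SD of the analysed BQSU score. The grand mean is 0.4, and the sum of squared deviations is 0.4² + 4 × 0.1² = 0.20. The noncentrality is λ = N × 0.20 / (1 − ρ), with 4 and 4(N − 1) df under compound symmetry. For N=56 and ρ=0.5, λ = 56 × 0.20 / 0.5 = 22.4. At 0.4 SD the sum is 0.32² + 4 × 0.08² = 0.128.

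| Nicotine vs saline | N | ρ=0.3 | ρ=0.5 | ρ=0.7 |
|---|---|---|---|---|
| 0.5 SD | 56 | 0.848 | 0.957 | 0.999 |
| 0.5 SD | 70 | 0.931 | 0.988 | >0.999 |
| 0.4 SD | 56 | 0.614 | 0.797 | 0.969 |
| 0.4 SD | 70 | 0.741 | 0.896 | 0.992 |

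**2. Non-significance when rate does something.** For a paired fastest-versus-slowest t test at two-sided 0.025, the noncentrality is dz√N, where dz is the difference in SDs of the paired difference. With dz=0.3 it is 0.3√56 = 2.24 or 0.3√70 = 2.51, and the test misses 52% / 41% of the time. If the 0.3 is in outcome SDs, dz = 0.3/√(2(1 − ρ)), and the miss rate is 28% to 65% / 17% to 56% for ρ from 0.7 to 0.3.

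**3. Why a bound alone is not enough.** Take an illustrative margin of 0.4 SD of the paired difference at one-sided 5%. If nicotine has no effect on urges at all, bounding only fastest versus slowest passes 82% / 91% of the time. Bounding all six rate differences and also requiring slowest better than saline (two-sided 0.025) passes under 1%.

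**4. Minute 0.** Section 9.A places the minute-0 assessment immediately before the infusion. Averaged over the five analysis times with equal weight, a constant post-infusion difference δ contributes (0 + 4δ)/5 = 0.8δ to the condition main effect. A condition-by-time term would recover it, but the BQSU text does not name one.

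**5. What a joint rule would cost.** This simulation uses pooled error with 4(N − 1) − 4 df. True rate differences are zero, slowest versus saline is 0.4 SD of the paired difference, and saline is tested at two-sided 0.025. The rule requires all six bounds plus the saline contrast, for one BQSU factor:

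| Margin | one-sided 5% | one-sided 2.5% | one-sided 1.25% |
|---|---|---|---|
| 0.4 SD | 37% / 60% | 22% / 44% | 10% / 28% |
| 0.5 SD | 66% / 82% | 56% / 77% | 44% / 69% |

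The last column matches a two-sided 0.025. For comparison, at margin 0.4 and one-sided 5% the fastest-versus-slowest bound alone passes 82% / 91%. The saline contrast alone passes 77% / 86%.

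**The case against.** Three stronger readings are tempting, and the documents do not support them.

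**That the BQSU analysis can say nothing about Hypothesis #1A.** The similar modelling approach carries over the active-rate contrasts and AIC curve fitting, so the model will give estimates of the curve's shape. A very large rate effect would count against the hypothesis informally. If saline is a factor level, the 4-df condition effect comprises 3 df among the rates and 1 df for saline against their mean. A significant condition effect with flat rate contrasts would then point to nicotine versus saline. All of this stands. It remains informal: it sets no bound, does not isolate the slowest rate, and leaves the active-rate contrasts on their own unable to tell equal relief from no relief.

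**That Hypothesis #1A and section 10 flatly contradict each other.** With saline as a level, a significant condition effect and minimal differences among active rates can both hold. The expectation sentence speaks of delivery rate, however, so it fits the hypothesis only if it refers to nicotine versus saline.

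**That listing minute 0 as an outcome necessarily weakens the test.** A baseline level with a condition-by-time term is an ordinary longitudinal layout, and the similar approach may be meant to include that term. The 80% figure applies only if it does not.

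It can also be said that bounding all six rate differences is stricter than the documents require. That is fair. The six-bound rule guards against a non-monotone pattern (equal ends, shifted middle) that nothing in the plan suggests, and it costs power. The mismatch in BQSU times is real, but it is a separate, smaller matter.

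**Conclusion.** The point holds as a statement about the decision rule. Neither significance nor non-significance of the planned BQSU condition effect establishes a minimal effect of rate with urge relief maintained. The test can be significant with high probability when rate has no effect (61% to over 99% across the cases in step 1), and it can miss a 0.3 SD paired difference about half the time. These sizes rest on assumed correlations, compound symmetry, no menthol term and, for step 1, saline being a level of the factor. If saline is not a level, a significant result could still reflect a rate difference small enough to count as minimal, because no bound is set. The margins are illustrations, not recommendations. This should be corrected before unblinding: the outcome belongs to the Specific Aim, and the data needed are already scheduled.

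**What to change.** In section 10:

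1. State that the condition factor has five levels, saline and four rates. Reword the BQSU expectation on rate: greater urge relief with nicotine than with saline, and minimal differences among the four active rates. The expectations on menthol preference can stay.
2. Use each session's minute-0 BQSU score as a covariate, not an outcome.
3. For each BQSU factor, report with confidence intervals the differences among the active rates (at least fastest versus slowest) and the slowest rate versus saline. State whether these are averaged over the post-infusion times or given at each time. Averaging over the five scheduled times (11, 30, 60, 90, 120) would shrink a difference confined to 11 minutes to one fifth.
4. Conclude that rate has a minimal effect with urge relief maintained only if two conditions are met: the prespecified rate interval or intervals lie within a margin that the sponsor justifies and fixes before unblinding, and the slowest rate relieves urges more than saline. Use a confidence level consistent with the plan's 0.025. Do not infer a minimal effect from non-significance. Say how the claim reads if the two BQSU factors disagree.
5. Reconcile the BQSU analysis times with Fig 2 (10 versus 11 minutes, and the unused 90-minute score).

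Whether to bound all six rate differences or only fastest versus slowest is the sponsor's choice. At margin 0.4 SD and one-sided 5%, the ends-only bound passes 82% / 91% of the time even if both middle rates differ from equal ends by 0.4 SD, against about 0.1% with six bounds. When all rates are truly equal, however, the six bounds pass only 46% / 67%.

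The cost is analysis wording, one justified margin and one confidence level, with no new visits or measurements. The downside is that the joint claim may be inconclusive, as the step 5 table shows. Estimates and intervals remain reportable in every case.
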